Appendix 2 Approach to model development

For each newly developed or revised risk prediction model, we fill adopt the following general approach to model development.

- 1. Potential predictors will be identified and patterns of missing data within the potential predictors will be explored, with particular attention to the completeness and accuracy of data linkage between the databases. Approaches to handling the missing data will be compared, based on the best performing approaches from previous work.
- The most appropriate functional form for each potential predictor will be explored, taking
 into consideration the use of continuous non-linear models (e.g. restricted cubic splines or
 right-restricted cubic splines) for continuous predictors and appropriate categorisation and
 structure of categorical predictors.
- 3. A main effects model will be fitted through a process of deleting terms, re-fitting and verifying, using: likelihood ratio tests to remove non-significant predictors; and the Bayesian Information Criterion (BIC)^[30] as the basis to determine which predictors make an important contribution to the fit of the model.
- 4. The functional form of each predictor included in the main effects model will then be reexamined to confirm if any changes are required based on adjustment for other important predictors.
- 5. Finally, interactions between the predictors will be introduced based on clinical input to identify and prioritise the potentially important interactions to consider and avoid over fitting, with interactions retained if they have a positive effect on the BIC.

For objectives 2a and 3a: the addition of new predictors to existing models will be considered and then the effect of those predictors previously included in the risk model will be re-assessed to determine whether they still make an important contribution to the model (see above).

For objectives 2b and 3b: the risk model will be re-fitted to the new outcome, predictors that were previously considered but were found not to be important predictors for hospital survival will be reassessed by adding them to the model and finally the effect of those predictors previously included in the risk model will be re-assessed to determine whether they still make an important contribution to the model (see above).

For objectives1a, 2b, 3b: it is anticipated that predictors representing age, chronic ill health and functional status will have a greater impact on longer term outcomes than on hospital survival, whereas predictors relating to the acute illness will have less impact.

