The occurrence of hyperglycaemia is common among critically ill patients, regardless of diabetes status, and is associated with acute severity of illness and outcomes.^[6] Critical illness-related hyperglycaemia has previously been linked with subsequent development of Type 2 diabetes in small cohorts,^[7, 8] and data linkage between the CMP and the National Diabetes Audit will permit us to explore this in a much larger cohort and establish whether acute severity of hyperglycaemia or other risk factors are associated with the likelihood of developing Type 2 diabetes.

The occurrence of acute kidney injury (or acute renal failure) is common among critically ill patients and associated with high mortality,^[9] and has been strongly linked with subsequent end-stage renal disease.^[10] Data linkage between the CMP and the UK Renal Registry will enable us to evaluate this relationship in the UK and develop risk models to predict the requirement for long-term renal replacement among survivors of critical illness in the UK.

Survivors of critical care experience significant morbidity with substantial resultant healthcare resource use and costs. ^[11] Data linkage with Hospital Episode Statistics (HES) will enable us to estimate the cost of subsequent hospitalisations and its association with severity and/or duration of critical illness and other risk factors.

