Little is known on longer-term outcomes following in-hospital cardiac arrest and data linkage to ONS will enable us to extend our risk models to predict longer term mortality.

Finally, data linkage with HES will enable us to estimate the cost of subsequent hospitalisations and its association with the measured risk factors.

2. Study aim and objectives

The aim of the proposed study is to better understand the epidemiology of, risk factors for and consequences of critical illness leading to improvements in the risk models used to underpin national clinical audits for adult general critical care, cardiothoracic critical care and in-hospital cardiac arrest using data linkage with other routinely collected data sources.

Specific objectives are:

- To improve risk models for adult general critical care by: (1a) developing risk models for
 mortality at fixed time-points and time-to event outcomes (by data linkage between the
 CMP and death registrations from ONS); developing risk models for longer term chronic
 health outcomes of (1b) diabetes (by data linkage between the CMP and the National
 Diabetes Audit) and (1c) end-stage renal disease (by data linkage between the CMP and the
 UK Renal Registry); and (1d) developing risk models for subsequent health care utilisation
 and costs (by data linkage between the CMP and HES)
- To improve risk models for cardiothoracic critical care by: (2a) enhancing risk factor data (by data linkage with the National Adult Cardiac Surgery Database); (2b) developing risk models for longer term mortality (by data linkage between the CMP and death registrations from ONS); and (2c) developing risk models for subsequent health care utilisation and costs (by data linkage between the CMP and HES)
- 3. To improve risk models for in-hospital cardiac arrest by: (3a) enhancing risk factor data (by data linkage between NCAA and HES); (3b) developing risk models for longer term mortality, health care utilisation and costs (by data linkage between NCAA and ONS); (3c) developing risk models for subsequent critical care utilisation (by data linkage between NCAA and CMP); and (3d) developing risk models for subsequent health care utilisation and costs (by data linkage between NCAA, ONS and HES)

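### The association questions on hyperglycaemia and acute kidney injury in section 1.1 have no analysis that guarantees an adjusted estimate, because the only stated model-building rule may delete those terms

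*Protocol*

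**What the plan says.** Section 1.1 sets two questions about association. The diabetes linkage is to "establish whether acute severity of hyperglycaemia or other risk factors are associated with the likelihood of developing Type 2 diabetes". The renal linkage is to "evaluate this relationship in the UK and develop risk models to predict the requirement for long-term renal replacement", so evaluating the relationship and building a prediction model are both named. The overall aim in section 2 is likewise to "better understand the epidemiology of, risk factors for and consequences of critical illness".

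The numbered objectives 1b and 1c in section 2 are narrower. They speak of "developing risk models for longer term chronic" health outcomes and name no exposure.

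Appendix 2 applies one procedure "For each newly developed or revised risk prediction model". Step 3 uses "likelihood ratio tests to remove non-significant predictors", with the BIC "as the basis to determine which predictors make an important contribution to the fit of the model". Step 2 considers splines for continuous predictors. Appendix 2 adds text specific to objectives 1a, 2a, 2b, 3a and 3b, but none for 1b or 1c. Sections 5.2.1.2 and 5.2.1.3 define outcome and population only. They name no exposure, keep no term in the model and describe no separate association analysis. Section 5.1.4 says that the analysis plans will be finalised before modelling.

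**The concern.** A deletion rule built for a compact prediction model asks whether a term earns its place given everything else in the model. An association question asks how large the adjusted effect is and how precisely it is known, whatever the answer. Under Appendix 2 the glucose or kidney-injury terms can leave the model, and then no adjusted estimate exists. If they stay, they do so because the estimate was large enough to pass a strict threshold, so the estimate and its interval are conditional on selection.

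Two features add to this. Appendix 1 extracts overlapping markers (lowest and highest glucose; lowest and highest creatinine, urea, urine output, renal support days), so one effect can be split over several terms and some of them deleted. The same rule can also remove confounders, such as body mass index or ethnicity, that an association model would keep on subject-matter grounds.

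**Working it through.** The protocol gives no event count, effect size, exposure prevalence, spline degrees of freedom or significance level for 1b or 1c, so there is no figure of its own to reproduce.

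**Inputs.** Section 3.2 gives 280,000 critical care unit survivors for model fitting. That is an upper limit, because 1b and 1c use hospital survivors after exclusions. I assume n = 250,000, 1% events (2,500; range 1,250 to 3,750) and 30% exposed.

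**BIC threshold.** A term with d parameters is kept if its likelihood ratio chi-square exceeds d × ln(n). ln(250,000) = 12.43; for n = 200,000 to 280,000 the range is 12.2 to 12.5.
- d = 1: 12.43, equivalent to p = 0.0004
- d = 3: 37.3, equivalent to p = 4 × 10⁻⁸
- d = 4: 49.7, equivalent to p = 4 × 10⁻¹⁰

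**Chance of being kept.** SE of the log odds ratio ≈ 1/√(events × q(1 − q)), where q is the proportion exposed. With 2,500 events this is 1/√(2,500 × 0.3 × 0.7) = 0.0436. For an odds ratio of 1.15, expected z = ln(1.15)/0.0436 = 3.20, so the noncentrality is 3.20² ≈ 10.3. Noncentral chi-square tail areas then give:

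| Events | Odds ratio | Power at 5%, 1 df | Kept by BIC, 1 df | Kept by BIC, 3 df |
|---|---|---|---|---|
| 1,250 | 1.15 | 62% | 10% | about 0% |
| 2,500 | 1.15 | 89% | 37% | under 1% |
| 3,750 | 1.15 | 97% | 65% | 2% |
| 2,500 | 1.2 | 99% | 74% | 4% |
| 2,500 | 1.3 | about 100% | 99% | 53% |
| 2,500 | 1.5 | about 100% | about 100% | about 100% |

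The 3-df column carries the same noncentrality on three parameters. It is the case where the extra parameters add no fit.

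**Rarer outcome, as 1c might be.** Assume n = 280,000, 0.1% events (280) and 20% exposed. Noncentrality = 280 × 0.2 × 0.8 × ln(OR)².
- OR 1.5: 7.37. Power at 5% is 77%; kept 20% at 1 df and about 0% at 4 df. If other terms in the model explain half the variance of the exposure, noncentrality halves to 3.68 and 1-df retention falls to 5%.
- OR 2.0: 21.5. Kept 86% at 1 df and about 1% at 4 df.
- OR 3.0: 54.1. Kept about 100% at 1 df and 68% at 4 df.

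**Exaggeration.** With 2,500 events, a 1-df estimate survives only if |z| exceeds √12.43 = 3.53, that is, if the estimated odds ratio exceeds exp(3.53 × 0.0436) = 1.17. For a true odds ratio of 1.15, the surviving log odds ratios average about 1.32 times the truth, giving a reported odds ratio of about 1.20.

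**Dependence on the penalty.** If the penalty uses events, as it can in the Cox models that section 5.1.4 lists, ln(2,500) = 7.82 (p = 0.005). Retention at OR 1.15 rises from 37% to 66% at 1 df, and at OR 1.3 from 53% to 91% at 3 df.

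**The case against.** The strongest reply is that 1b and 1c, as numbered, are prediction objectives, and that LR/BIC deletion is a sound way to build a prediction model from a very large sample. That stands. A reader of section 1.1 might infer that the objectives themselves ask the association question. They do not; the question is posed in the background and, more broadly, in the overall aim.

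A reader might also infer that a deleted exposure will be reported as having no association. The protocol does not say so. Appendix 2 speaks only of importance to model fit, and step 2 examines the functional form of each candidate predictor before any deletion.

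Size is a fair objection too. Larger effects survive as one-parameter terms (OR 1.3 with 2,500 events: 99%). Section 1.1 describes the link between kidney injury and later renal failure as strong; with an assumed 500 events, 20% exposed and an odds ratio of 3, retention exceeds 99% for one to four parameters. Step 2 considers splines without requiring them, so the severe multi-parameter thresholds need not apply.

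Finally, naming exposures and confounders is ordinary analysis-plan detail, and the plans were still to be finalised. That lowers the weight of the point but does not remove it. The protocol fixes one rule for all models, and that rule does not answer a question the protocol says the linkage will answer.

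**Conclusion.** The point holds as a mismatch between stated purpose and stated method, of moderate weight. It is not an error in the risk models. Section 1.1 promises an answer on two associations, and nothing in sections 5.2.1.2, 5.2.1.3 or Appendix 2 ensures that the exposures stay in the model or that an estimate free of selection is reported. The practical risk lies with modest effects, multi-parameter terms, rare outcomes and overlapping markers. It is small for strong effects with many events. All retention figures rest on assumed event counts, prevalences and effect sizes, and most on a penalty based on the number of patients; retention is higher if events are used. The documents do not support the claim that a real association will be declared absent, or that a strong one is likely to be lost.

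**What to change.** Keep LR/BIC deletion for the risk models. In sections 5.2.1.2 and 5.2.1.3, or in the analysis plan that section 5.1.4 announces, add one pre-specified association model for each objective:
- **1b:** retain the named glucose terms and a fixed confounder set, irrespective of LR tests and BIC.
- **1c:** retain the named acute kidney injury terms (for example creatinine, urine output and renal support) and a fixed confounder set, on the same basis, with a joint test for the correlated renal markers.
- **Both:** report the adjusted effect with its 95% CI from that model, and state that deletion from the risk model is not evidence of no association.

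The confounder sets can be agreed with the Clinical Advisory Groups before modelling. The cost is some wording and one extra model per objective; no further data are needed, because the example terms are already in Appendix 1. If the analysis plan, which is not available here, already contains such models, a cross-reference is enough.
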